6.2.3 Handling of Missing Data

Missing data will not be imputed unless otherwise specified elsewhere in the SAP. Missing dates or partially missing dates will be imputed conservatively for adverse events and prior/concomitant medications/procedures. Specific rules for handling of missing or partially missing dates for adverse events and prior/concomitant medications/procedures are provided in [Appendix 1](#).

By-visit endpoints will be analyzed using observed data, unless otherwise specified. For observed data analyses, missing data will not be imputed and only the observed records will be included.

6.2.4 Handling of Treatment Cycles

In arm C, patients will be treated in a 28 days cycle. The schedule of each cycle will not change for dose delays or dose holds.

During maintenance treatment in Arms A and B, patients will be treated in a 28 days cycle. The schedule of each cycle will not change for dose delays or dose holds.

6.2.5 Adjustment for Covariates

No covariates will be adjusted in primary analyses.

6.2.6 Data Integrity

Before the final statistical analysis begins, the integrity of the data should be reviewed to assure fit-for-purpose. The data set for analysis should be an accurate and complete representation of the patients' relevant outcomes from the clinical database. All data should be complete and reviewed up to a pre-specified cutoff date. Consistency checks and appropriate source data verification should be complete.

6.3 PATIENT CHARACTERISTICS

6.3.1 Patient Disposition

The number (percentage) of subjects treated, discontinued from study treatment, entered efficacy and survival follow-up phase, discontinued from study and duration of follow-up will be summarized. The primary reason for treatment and study discontinuation will be summarized according to the categories in the eCRF.

6.3.2 Protocol Deviations

Major protocol deviation criteria will be established and patients with major protocol deviations will be identified and documented before the database lock. Major protocol deviations will be

summarized for all patients in the Safety Analysis Set. They will also be presented in a listing by each category.

6.3.3 Demographic and Other Baseline Characteristics

Demographic and other baseline characteristics will be summarized using descriptive statistics in the Safety Analysis Set.

Continuous variables include:

- Age (years)
- Time (weeks) from initial diagnosis of glioblastoma to first dose date
- Time (weeks) from initial surgical resection

Categorical variables include:

- Age group (< 65, ≥65 years)
- Gender (Male, Female)
- Race (Asian, Black or African American, White, others)
- ECOG performance status (0, 1)
- Surgical status for initial diagnosis of glioblastoma (biopsy, partial resection, complete resection and no prior surgery)
- Baseline corticosteroids use (yes, no)
- Relapse status (arm C only)
- MGMT promoter status (arm C only)
- Prior use of temozolomide (arm C only)
- WHO grade at initial diagnosis (arm C only)

6.3.4 Prior and Concomitant Medications

Prior and concomitant medications will be coded using the version of World Health Organization Drug Dictionary (WHO DD) drug codes currently in effect at Beigene at the time of database lock and will be further classified to the appropriate Anatomical Therapeutic Chemical (ATC) code.

The number (percentage) of patients reporting prior and concomitant medications will be summarized by ATC medication class and WHO DD preferred term by phase in the Safety Analysis Set. Prior medications are defined as medications that started before the first dose date. Concomitant medications will be defined as medications that (1) started before the first dose of study treatment and were continuing at the time of the first dose of study treatment, or (2) started on or after the date of the first dose of study treatment up to 30 days after the patient's last dose or initiation of a new anti-cancer therapy. A listing of prior and concomitant medications will be provided.

6.3.5 Prior GBM Related Therapy (arm C only)

The number (percentage) of prior GBM related anti-cancer systemic therapies, surgical history and radiation therapy will be summarized in the Safety Analysis Set.

6.3.6 Medical History

Medical History will be coded using MedDRA (version currently in effect at BeiGene at the time of database lock). The number (percentage) of patients reporting a history of any medical condition, as recorded on the CRF, will be summarized by system organ class and preferred term in the Safety Analysis Set. A listing of medical history will be provided.

6.4 EFFICACY ANALYSIS

The primary efficacy analysis will be conducted when mature response data have been observed, which will be determined by the Sponsor.

An independent read of the tumor scans by Independent Review Committee (IRC) was planned at the beginning stage of the study. Following sample size reduction and due to the nonrandomized and nonregistrational nature of the study, the decision was made that independent reads would not be requested and investigator-evaluated assessments would be used to calculate ORR, DCR, CBR, DOR and PFS.

6.4.1 Primary Efficacy Endpoints

Efficacy analysis will be performed on all patients for all arms. For Arm A and Arm C, phase 1b and phase 2 are presented in different table columns.

Arm A and Arm B

Modified Disease Control Rate is the primary efficacy endpoint in Arms A and B. It is defined as the proportion of patients with CR, PR or SD per RANO criteria as the response assessment at the end-of-treatment (EOT) visit, as scheduled per protocol. Patients with no EOT tumor assessment, as scheduled per protocol (due to any reason), will be considered non-responders for modified DCR. Modified DCR of Pamiparib combination therapy is assumed as 60% in the study population. The historical rate in a similar population is estimated as 40% (Rivera et al., 2010). No formal hypothesis testing will be performed. Two-sided binomial exact 80% and 95% CI of modified DCR will be constructed to assess the precision of the rate estimate.

Arm C

Objective Response Rate (ORR) is the primary efficacy endpoint in arm C. The analysis will be performed for the efficacy analysis set. It is defined as proportion of patients with best overall response of CR or PR per RANO criteria (confirmed by a subsequent tumor assessment at least four weeks apart). Best overall response will be assessed from the start of study treatment until data cut-off date, disease progression or start of new anti-cancer therapy. Patients without postbaseline tumor assessment is considered nonresponders. ORR of Pamiparib combination therapy is assumed as 25% in the study population. The historical rate in a similar population is

estimated as 10% (Chen et al, 2013). Two-sided binomial exact 80% and 95% CI of ORR will be constructed to assess the precision of the rate estimate.

In addition, the number (%) of the best overall response categories (CR, PR, SD, PD) will be presented.

6.4.2 Secondary Efficacy Endpoints

Disease Control Rate (DCR – for arm C)

DCR is defined as the proportion of patients with best overall response of CR, PR or SD per RANO criteria. CR or PR will be confirmed by a subsequent tumor assessment at least four weeks apart. DCR will be performed in similar fashion as described in primary endpoint modified DCR on Efficacy Analysis Set.

Objective Response Rate (ORR – for arm A&B)

ORR for arm A&B will be performed for Efficacy Analysis Set in similar fashion as in primary endpoint for arm C.

Progression-Free Survival (PFS)

PFS is defined as the time from the first dose date to disease progression per RANO criteria or death, whichever occurs first. PFS analysis will be performed for all arms using Safety Analysis Set.

PFS censoring rule will follow FDA *Guidance for Industry, Clinical Trial Endpoints for Approval of Cancer drugs and Biologics* (2007). The censoring rules are described in Table 1. If a patient meets the criteria for more than 1 censoring rule, PFS will be censored at the earliest censoring date.

Table 1 Censoring Rules for Analysis of Progression-Free Survival

Censoring Categories	Date of Progression or Censoring	Outcome
Progression documented on scheduled visit or between scheduled visits	Date of first PD assessment	Progressed
Death before first tumor assessment	Date of death	Progressed
Death between scheduled adequate assessment visits	Date of death	Progressed
No baseline or postbaseline tumor assessments	Date of the first dose	Censored
No PD or death at the time of data cut-off or withdrawal from study	Date of last adequate radiologic tumor assessment prior to or on date of data cut-off or withdrawal from study	Censored

New anticancer treatment started	Date of last adequate radiologic tumor assessment prior to or on date of new anticancer treatment	Censored
Death or PD immediately after two or more missed visits	Date of last adequate radiologic tumor assessment before missed tumor assessments	Censored

CR = complete response, PD = progressive disease, PR = partial response, SD = stable disease
Adequate tumor assessment is a radiologic assessment of CR, PR, SD, non-CR/non-PD or PD as determined by investigators.

Duration of Response (DOR)

DOR is defined as the time from the date of the earliest documented response (confirmed or unconfirmed) of CR or PR to disease progression or death for any cause, whichever occurs earlier. Only responders will be included in the DOR analysis. Censoring rule for DOR will follow PFS censoring rule.

Overall Survival (OS)

OS is defined as the time from the date of first study treatment to death of any cause. Patients who have not died by the analysis cutoff date will be censored at the last date known to be alive or the data cutoff date, whichever is earlier. OS will be performed for Safety Analysis Set.

Time-to-event variables PFS, OS and DOR will be estimated using the Kaplan-Meier (KM) method. KM estimates of PFS, DOR and OS will be plotted over time. Median PFS, DOR and OS, if possible to estimate, in each arm will be presented, along with their 2-sided 95% CIs using Brookmeyer and Crowley method (Brookmeyer & Crowley, 1982). The PFS-6m, PFS-12m, OS-6m, and OS-12m, defined as the proportion of patients in the Safety Analysis Set who remain alive and progression-free at 6 months and 12 months (or alive at 6 month and 12 months for OS), will be estimated using KM method along with the corresponding 95% confidence interval constructed using Greenwood's formula (Greenwood, 1926).

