11.2.5.2. Secondary Efficacy Analysis

Descriptive statistics will be used to summarize the secondary efficacy analysis.

DCR is defined as the proportion of patients with best overall response (BOR) of CR, PR, or SD. BOR is defined as the best response recorded from the start of study treatment until data cutoff or start of new anticancer therapy.

CBR is defined as the proportion of patients with BOR of CR, PR, or durable SD (SD \geq 24 weeks).

Exact 95% CIs will be calculated for the rate variables: ORR for patients with measurable disease at baseline, DCR, and CBR in the Safety Analysis Set.

PFS is defined as the time from the date of first study treatment to disease progression or death, whichever occurs first.

PFS censoring rule will follow [FDA Guidance for Industry, Clinical Trial Endpoints for Approval of Cancer Drugs and Biologics \(2007\)](#). Patients who have a clinical determination of progression should undergo an MRI, if possible, to correlate radiographic findings with the clinical findings.

Data for patients without disease progression or death at the time of analysis will be censored at the time of the last tumor assessment. Data for patients who are lost to follow-up prior to documented disease progression will be censored at the last tumor assessment date when the patient was known to be progression-free. Data for patients who started new anticancer therapy will be censored at the last tumor assessment date prior to the introduction of new therapy. More details will be given in the SAP.

DOR is defined as the time from the date of the earliest documented response to disease progression or death for any cause, whichever occurs earlier. Only responders will be included in the DOR calculation.

OS is defined as the time from the date of first study treatment to death of any cause.

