Appendix Table 3: Schedule of Assessments for Arm C (Pamiparib and Temozolomide) (Continued)

Study Phase	Screening ^a	Treatment ^b								End of Treatment ^c	Safety Follow-up ^d	Long-Term Follow-up ^d
		Cycle 1				Cycle 2		Cycle ≥3				
		D1	D8	D15	D22	D1	D15	D1	D15			
Concomitant medication(s) ^p	X	X	X	X	X	X	X	X	X	X	X ^p	X (~q12w) ^p
Pharmacokinetics ^q		X		X								
Blood for biomarkers ^r	X	X		X				X		X		
Tumor tissue ^s	X											
Survival follow-up												X (~q12w)

7/-14 to -1, Day -7/-14 to Day -1 of screening; aPTT, activated partial thromboplastin time; CSF, cerebrospinal fluid; D, day; ECG, electrocardiogram; ECOG, Eastern Cooperative Oncology Group; INR, International Normalized Ratio; MRI, magnetic resonance imaging; q8w ±7d, every 8 weeks ± 7 days; ~q12w, approximately every 12 weeks

^a Screening must occur within 28 days of Day 1. Assessments obtained within 14 days of Day 1 (pregnancy and laboratory assessments: within 7 days) do not have to be repeated on Day 1. Some assessments have a narrower screening window as shown in the table. It is highly recommended that general screening assessments such as physical examination and laboratory assessments should be conducted first to rule out ineligibility based on those grounds before more involved and/or invasive procedures are carried out.

^b Cycle 1 encompasses the dose-limiting toxicity (DLT) assessment window, and assessments of Day 1 of Cycle 2 at the end of the DLT assessment window are required for a patient to be DLT-evaluable. Assessments shown for Cycle 3 apply to all subsequent cycles except for MRI that occurs every second cycle (every 8 weeks).

^c The end-of-treatment (EOT) visit will occur within 7 days after a patient discontinued study treatment for any of the reasons outlined in [Section 6.5.1](#). A visit should be scheduled as soon as possible, but the EOT visit may occur later after discussion with the medical monitor for specific circumstances, such as prolonged hospitalization. The visit at which MRI showed progressive disease (PD) may be used as the EOT visit provided that all required assessments were performed. MRI does not have to be repeated if it was performed within 14 days of the EOT visit or at a prior response evaluation that documented PD. ECG does not have to be repeated if it was performed within 14 days of the EOT visit.

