- ⁱ Testing will be performed by the local laboratory at Screening and will include HBV serology (HBsAg, HBsAb, and HBcAb) and viral load assessment (HBV DNA).
- ^j Urinalysis will be assessed using urine dipstick. Urine microscopy will be performed if any assessment on the urine dipstick is abnormal. Urinalysis includes glucose, protein, ketones, bilirubin, blood, red blood cells, and white blood cells.
- ^k For women of childbearing potential, a serum pregnancy test must be performed during screening ≤ 7 days prior to Day 1. For subsequent pregnancy testing while on study treatment and at end of treatment, urine pregnancy tests are acceptable. If a urine pregnancy test is positive, a confirmatory serum pregnancy test is required.
- ^l Tumors will be assessed at screening by MRI per RANO criteria within 14 days prior to Day 1, then every 8 weeks (± 7 days) and as part of the EOT visit. Patients without PD at the EOT visit must then be followed with MRIs every 8 weeks (± 7 days) during the Follow-up Phase.
- ^m All patients will receive daily pamiparib as outlined in [Section 4](#). Patients will continue receiving pamiparib in combination with TMZ in Arm C until PD, unacceptable toxicity or death, withdrawal of consent, loss to follow-up, or study termination by sponsor. Patients will be required to fast for at least 1 hour before and 2 hours after each pamiparib administration. Water is allowed during the fasting period. A dose of pamiparib should be skipped if it is not taken within 2 hours of the scheduled time. An extra dose of pamiparib should not be taken to make up for a missed dose. If vomiting occurs during the course of treatment, no re-dosing of the patient is allowed before the next scheduled dose. On days with PK assessments, pamiparib should be administered in the clinic.
- ⁿ All patients will receive temozolomide (TMZ) at a dose level as outlined in [Section 4](#). TMZ will be given for Days 1 to 21 of each 28-day cycle. Instructions for TMZ administration are the same as for pamiparib. Antiemetic prophylaxis may be provided as described in [Section 7.1.2.3](#). On days with PK assessments, TMZ should be administered in the clinic.

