6 STATISTICAL METHODS

6.1 ANALYSIS POPULATIONS

Safety Analysis Set: includes all patients who received any dose of any of the study treatments (pamiparib, RT and/or TMZ). The Safety Analysis Set will be used for efficacy and safety analyses.

Efficacy Analysis Set: includes all patients in the Safety Analysis Set who:

Arms A & B: had a tumor assessment at baseline and at End of Treatment unless discontinued treatment or study early due to disease progression or death prior to tumor assessment.

Arm C: had measurable disease at baseline and at least one postbaseline tumor assessment unless discontinued treatment or study early due to disease progression or death prior to tumor assessment.

DLT-Evaluable Analysis Set: includes patients from escalation cohorts only in the Safety Analysis Set who received ≥ 42 Gy of RT (Arms A and B) and $\geq 70\%$ of scheduled pamiparib (Arms A, B and C) and TMZ (Arms B and C) during the DLT assessment window. All patients who had a DLT event will be considered DLT-evaluable regardless of study treatment intensity.

PK Analysis Set: includes all patients for whom valid pamiparib PK parameters can be estimated.

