CBR (clinical benefit rate) is defined as the proportion of patients with best overall response of CR, PR or SD \geq 24 weeks per RANO criteria. CR or PR will be confirmed by a subsequent tumor assessment at least four weeks apart.

BOR (best of response) is defined as the best response recorded from the start of study treatment until data cutoff, or start of new anti-cancer therapy. Computation of BOR will consider timepoints prior to PD when determining BOR.

Time to event data

OS (overall survival) is defined as the time from the first dose date to date of death for any cause. Patients that are still alive at the time of analysis will be censored at the last contact date that is known to be alive.

PFS (progression free survival) is defined as the time from the first dose date to disease progression per RANO criteria or death, whichever occurs first. Censoring rules for PFS are described in Table 1 in [section 6.4.2](#).

DOR (duration of response) is defined as the time from the date of the earliest documented response to disease progression or death for any cause whichever occurs earlier.

All calculations and analyses will be conducted using SAS version 9.4 or higher.

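### Arm C DCR sets no minimum time from first dose for stable disease, so one early SD scan in a patient who stops for toxicity can count as disease control

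*SAP*

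**What the plan says.** - SAP 6.4.2, Arm C: "DCR is defined as the proportion of patients with best overall response of CR, PR or SD per RANO criteria". Confirmation at least four weeks apart is required for CR and PR only.
- SAP 6.2.1: BOR "is defined as the best response recorded from the start of study treatment until data cutoff, or start of new anti-cancer therapy", and "Computation of BOR will consider timepoints prior to PD when determining BOR". An SD followed by PD therefore stays SD.
- The only duration requirement for SD belongs to a different endpoint. Protocol 11.2.5.2 defines CBR through "CR, PR, or durable SD", meaning SD of at least 24 weeks.
- Analysis set, SAP 6.4.2: "DCR will be performed in similar fashion as described in primary endpoint modified DCR on Efficacy Analysis Set". SAP 6.1 limits the Arm C set to patients who "had measurable disease at baseline and at least one postbaseline tumor assessment unless discontinued treatment or study early due to disease progression or death". Stopping for toxicity is not among the exceptions.
- Protocol Appendix Table 3, footnote c: "The end-of-treatment (EOT) visit will occur within 7 days after a patient discontinued study treatment for any of the reasons outlined in" Protocol 6.5.1, which lists adverse events. The visit may be later by agreement with the medical monitor. Footnote l schedules MRI at screening, every 8 weeks ± 7 days, "and as part of the EOT visit. Patients without PD at the EOT visit must then be followed" with further MRIs every 8 weeks.
- Two rules govern when the EOT MRI may be omitted. Protocol 6.5.2 and Appendix Table 3 footnote c waive it if an MRI was done within 14 days of the EOT visit. Protocol 8.3.1 asks for a repeat only if more than 4 weeks have passed since the last evaluation.

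**The concern.** Disease control is normally read as no progression through at least the first planned assessment. Here nothing ties SD to that assessment. A patient taken off treatment in week 4 for toxicity can have an EOT scan a few days later, only weeks after baseline. Enhancing disease may grow by up to just under 25% and still meet that part of the SD definition (Protocol Appendix Table 6). If the scan reads SD, the patient is a success for good, whatever the next scan shows.

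An early treatment failure can therefore raise a named secondary endpoint of Arm C (SAP 4.2). The error runs in one direction. Modified DCR in Arms A and B does not have this gap, because it is tied to the EOT visit as scheduled.

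**Working it through.** The documents give no expected value for Arm C DCR, so there is no stated figure to reproduce. The check covers when an early scan can arise, how it is scored, and what it does to the rate.

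**1. First scheduled scan.** Appendix Table 3 places the first on-treatment MRI at Cycle 3 Day 1, Study Day 57, ± 7 days.
- Window: Day 57 − 7 = Day 50 to Day 57 + 7 = Day 64.
- In days since first dose, the earliest is 56 − 7 = 49, which is Day 50.

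**2. When an EOT MRI falls due before Day 50.** The screening MRI is on Day −14 to Day −1 and there is no Day 0 (Protocol 6.3). From a screening MRI on Day d (negative) to an EOT visit on Day t, the elapsed time is t − d − 1 days. If the screening MRI counts as the last MRI (the documents do not say), the scan is due once this exceeds the waiver:

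| Rule | Screening MRI Day −14 | Screening MRI Day −1 |
|---|---|---|
| 14 days | t + 13 > 14, from Day 2 | t > 14, from Day 15 |
| 4 weeks | t + 13 > 28, from Day 16 | t > 28, from Day 29 |

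The exposed period runs from these days to about Day 49. It starts by Day 15 (week 3) under the 14-day rule and by Day 29 (week 5) at the latest under the 4-week rule. The EOT visit may follow stopping by up to 7 days, so the day of stopping can be up to a week earlier. Both rules only excuse a scan and do not forbid one. Protocol 6.4 and 8.3.1 also call for an MRI whenever progression is suspected, and such a scan can also read SD.

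**3. How a toxicity stopper is scored under the current text.**
- Early scan reads SD: in the set, counted as disease control, and kept if PD follows.
- Early scan reads PD, or is not evaluable with no later response: in the set, not a success.
- No postbaseline scan: outside the Efficacy Analysis Set, so removed from the denominator.

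**4. Effect on the rate.** SAP 5 gives n = 30 for the Arm C expansion cohort; assume all 30 are in the set.
- One patient: 1/30 = 3.3 points. Five patients: 5/30 = 16.7 points. The count of 1 to 5 is an assumption.

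Illustration, assuming 12 other patients are controlled and 3 stop for toxicity with no assessment on or after Day 50 (exact Clopper-Pearson intervals):

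| Handling of the 3 stoppers | DCR | 80% CI |
|---|---|---|
| Early SD counted as control (current text) | 15/30 = 50.0% | 37.0 to 63.0 |
| No scan, dropped from the set (current text) | 12/27 = 44.4% | – |
| Kept as non-successes | 12/30 = 40.0% | 27.7 to 53.3 |

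Both outcomes under the current text lie above the last row.

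**The case against.** A reader might infer that every early stopper has an MRI within days and is then scored as disease control, so that the first weeks of toxicity feed straight into DCR. The documents do not support that. The 14-day and 4-week rules can excuse the EOT MRI, the visit can be delayed, and a toxicity stopper with no postbaseline scan is dropped from the set, not counted as a success. That is a separate bias with its own remedy.

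SD is not automatic either. Appendix Table 6 also requires stable or reduced T2/FLAIR, no new lesion, stable or reduced corticosteroids, and stable or improved clinical status. Appendix Table 5 makes the lesion response not evaluable if the glucocorticoid dose varied over the 5 days before the scan.

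The size is unknown. No early discontinuation rate is given for this combination. The nearest figure is 3 of 45 patients stopping pamiparib monotherapy for an adverse event (Protocol 1.3.5.3), which covers a different regimen and is not limited to early stops. Patients without PD at EOT continue on 8-weekly MRIs, so some early SDs are followed by a valid later one and add no bias.

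Finally, DCR is secondary and descriptive, no decision rests on it, and CBR and PFS are also reported. Protocol and SAP agree on the definition, and Appendix 2 sets no minimum SD interval.

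These points narrow the finding and limit its weight. They do not remove it. The exposed weeks remain under either waiver, an early SD still counts, and CBR and PFS do not correct the DCR figure itself.

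**Conclusion.** The point holds in a limited form. Arm C DCR has no minimum SD interval, so a patient who stops for toxicity in roughly weeks 3 to 7 and whose EOT or unscheduled scan reads SD is counted as disease control, even if the next scan shows PD. Each such patient without a later qualifying assessment adds 3.3 points at n = 30. The total depends on a number the documents do not give: 1 to 5 patients, an assumption, would be 3.3 to 16.7 points. A firm overstatement of 10 to 20 points might be inferred by supposing 3 to 6 such patients, but nothing in the documents supports that count, and it ignores those still stable at a later scan.

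The start of the exposed period also assumes that the screening MRI counts toward the waivers. If it does not, exposure begins earlier. The bias is upward, on a secondary descriptive endpoint. It is worth correcting in the SAP but does not threaten the primary analysis.

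**What to change.** In SAP 6.2.1 and 6.4.2:
- For Arm C DCR, count SD toward BOR only if it is documented at least 49 days after first dose (8 weeks minus the 7-day window, so Day 50 or later).
- Report an earlier SD with no later qualifying assessment as not evaluable, and keep the patient in the denominator as a non-success. The BOR table in SAP 6.4.1 lists only CR, PR, SD and PD, so it needs a not-evaluable row.
- Treat toxicity stoppers with no postbaseline scan the same way for DCR, so that the SAP 6.1 set definition does not drop them.
- Record the change in SAP Section 8, because the protocol has the same DCR definition.

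In the protocol, the 14-day passages (6.5.2 and Appendix Table 3 footnote c) and the 4-week passage (8.3.1) on the EOT MRI must be reconciled, including whether the screening MRI counts.

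Cost: wording changes and no new data. The reported DCR may be lower. A patient who is genuinely stable but starts new anticancer therapy before Day 50 would count as a non-success. The 49-day threshold is a choice, but it comes from the protocol's own scan window.
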